#### INSTRUCCIONES: Pídale al participante que elija la palabra que describa la IV. duración del dolor oral al deglutir y la respuesta.

Continuo \_\_\_\_\_ Periódico (Se viene y se va) \_

Global Scale-0 to 10 Scales Numeric Rating Scales (0-10) for Oral Pain, Sensitivity, and Dryness DOLOR ORAL

En una escala del 0 al 10, ¿qué tanto DOLOR siente en su boca en este momento? Por favor marque el número adecuado con un círculo.

0 1 2 3 4 5 6 7 8 9 10

No siento dolor

El peor que he sentido

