## 3.5.3 Visual analogue scales for subject reported oral pain, oral sensitivity, and oral dryness

Subject reported oral pain, oral sensitivity, and oral dryness will be captured through use of a 0 to 10 visual analogue scale (VAS) anchored with the words "no pain" to "worst pain" (Appendix C). We will use this VAS to evaluate these symptoms over treatment.

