## 11.6.2 Informed consent of Spanish speaking subjects

We anticipate the enrollment of Spanish speaking research participants into our study. The IRB approved full consent document will be translated into that language in accordance with the Clinical MAS Policy M77-2.

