#### **ORAL DRYNESS**

#### On a 0 to 10 scale, how DRY is your mouth NOW? Please circle the number.

0	1	2	3	4	5	6	7	8	9	10	

No dryness

Worst dryness

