## **15.10** APPENDIX J: SPANISH LANGUAGE TRANSLATIONS OF THE PATIENT-REPORTED OUTCOME FORMS

	Painor	neter (F			
Date: Signat	//	/	Time:	Timepoint:	LIP: [name] LIP

I INSTRUCCIONES: Pídale al participante que elija palabras de la lista de intensidad del dolor Sensorial tanto como de la lista de intensidad de dolor Afectivo a continuación, para describir el dolor oral en estos momentos. Haga un círculo alrededor de la letra y palabra y del número y palabra de las listas a continuación.

SENSORIAL	AFECTIVO
A Calambre	1. Irritante
B. Leve	2. Agobiante
C. Enloquecedor	3. Fastidioso
D. Ardor	4. Molestoso
E. Adolorido	5. Mortal
F. Punzante	6. Fatigoso
G. Que irradia	7. Insoportable
H. Que duele	8. Deprimente
I. Triturante	9. Espantoso
J. Resentido	10. Miserable
K. Como puñaladas	11. Torturante
O. Agudo	
P. Desgarrante	

Q. Insistente

II. INSTRUCCIONES: Pídale al participante que elija la palabra que describe la duración del dolor oral y marque la respuesta:

Continuo

Periódico (Se viene y se va) \_

III. INSTRUCCIONES: Pídale al participante que elija palabras del listado de intensidad del dolor Sensorial y del dolor Afectivo a continuación, para describir el dolor oral al deglutir. Marque con un círculo las letras/números y los números/palabras de estas listas.

SENSORIAL	AFECTIVO
A Calambre	1. Irritante
B. Leve	2. Agobiante
C. Enloquecedor	3. Fastidioso
D. Ardor	4. Molestoso
E. Adolorido	5. Mortal
F. Punzante	6. Fatigoso
G. Que irradia	7. Insoportable

- H. Que duele 8. Deprimente 9. Espantoso I. Triturante 10. Miserable J. Resentido
- K. Como puñaladas
- L. Agudo M. Desgarrante
- N. Insistente

- 11. Torturante

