#### SENSIBILIDAD ORAL

En una escala del 0 al 10, ¿qué tan SENSIBLE siente su boca en este momento? Por favor marque el número adecuado con un círculo.

0	1	2	3	4	5	6	7	8	9	10
No suf sentido		ensibilid	lad						La pec	or sensibilidad que he

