#### **RESEQUEDAD ORAL**

En una escala del 0 al 10, ¿qué tan SECA siente su boca EN ESTE MOMENTO? Por favor marque el número adecuado con un círculo.

0 1 2 3 4 5 6 7 8 9 10 No siento resequedad La peor resequedad que he sentido

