## Numeric Rating Scales (0-10) for Oral Pain, Sensitivity, and Dryness

#### ORAL PAIN

## On a 0 to 10 scale, how PAINFUL is your mouth now? Please circle the number.

	0	1	2	3	4	5	6	7	8	9	10
No pa	in										Worst pain

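### The three Spanish 0–10 symptom scales end at the worst the patient has felt, a self-referenced anchor that the English scales do not carry

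*Combined protocol and SAP*

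**What the plan says.** Section 3.5.3 describes the patient-reported pain, sensitivity and dryness scales as running from 0 to 10, names no pain and worst pain as the end points, and says they will be used to evaluate these symptoms over treatment. Appendix C prints the English forms. Each asks about the present (for pain, "how PAINFUL is your mouth now? Please circle the number") and ends at worst pain, worst sensitivity or, for the third, "Worst dryness".

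The ratings serve secondary objective 1.1.2.1. Section 6.2 also has the severity scales correlated with symptom-oriented instruments, and Section 10.2 uses other scales to judge whether a 25% fall in OMRS is a meaningful response.

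Section 11.6.2 states: "We anticipate the enrollment of Spanish speaking research participants into our study". Appendix J supplies their forms. The Spanish pain scale ends at "El peor que he sentido" and the dryness scale at "La peor resequedad que he sentido". The sensitivity anchor is broken across lines in the available text, but the fragment "or sensibilidad que he" and the closing participle are both there, so it reads the same way.

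The Painometer is also translated in Appendix J. In the first Spanish list (present pain) the last three sensory words are lettered O, P and Q, for example "P. Desgarrante". In the second list (pain with swallowing) the same words are lettered L, M and N, as in English.

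**The concern.** A 0–10 rating means something only relative to its end points. If one language group rates against worst pain and the other against the worst they have personally felt, the same number need not describe the same state. The Spanish wording tells a patient who is at a personal worst today to circle 10. If that patient is worse still at the next visit, 10 is again the answer and the deterioration is not recorded.

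The page labelled as the English version translation of Appendix J shows the English anchors. Someone checking equivalence from that page would therefore not see the difference. Ratings already given against the Spanish anchor cannot be converted afterwards. At stake are secondary objective 1.1.2.1 and the instrument work of Sections 6.2 and 10.2.

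**Working it through.** **1. The forms side by side.**

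| Scale | English upper anchor (Appendix C, repeated on the English version of Appendix J) | Spanish upper anchor (Appendix J) | Added in Spanish |
|---|---|---|---|
| Pain | worst pain | "El peor que he sentido" | that I have felt |
| Sensitivity | worst sensitivity | worst sensitivity that I have felt (line broken) | that I have felt |
| Dryness | "Worst dryness" | "La peor resequedad que he sentido" | that I have felt |

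The time frame (now) and the numbers 0 to 10 agree in both languages. The addition is the same on all three scales, so it is not a slip on one line.

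**2. What the addition does to a change score.** Take a patient at a personal worst on day 0 who is worse on day 14. Read literally, the Spanish form gives 10 and then 10, so the recorded change is 10 − 10 = 0. The English form does not tell a patient that a personal worst is a 10. The patient may circle a lower number and keep room above it.

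**3. What cancels and what does not.** Suppose the Spanish anchor adds a constant δ to every rating by a given patient. The change from day 0 to day 14 is then

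(Y14 + δ) − (Y0 + δ) = Y14 − Y0,

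so a constant shift drops out. Two things do not drop out: truncation at 10, and an anchor that moves when the patient reaches a new personal worst. If the correlations in Section 6.2 use raw scores, even a constant δ carried by some patients and not others stays in the data.

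**4. Whether a size can be computed.** For a raw-score difference between arms, the displacement would be δ × (k1 − k0) / 17, where k1 and k0 are the Spanish-form users in each arm of 17. The documents give neither δ nor k1 and k0, so no figure follows from them.

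**5. The Painometer letters.** The sensory weights in Appendix E sum to 4+1+5+4+1+5+3+2+4+3+5+5+5+2 = 49. Section 3.5.2 states a maximum of 48, which this sum does not reproduce. That is a separate discrepancy, and nothing here depends on it. The key runs from A to N and has no O, P or Q. However, Section 3.5.2 adds the weights of the selected words, the key prints each word beside its letter, and the Spanish instruction for the first list has both letter and word circled. Under that rule all 14 words have a weight.

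**The case against.** The best defence is that the English anchor is not firmly fixed either. It does not say worst possible or worst imaginable, and an English reader may also take it as the worst they have known. The diary in Appendix I does say worst possible, but it is a different instrument and does not settle how Appendix C is read. Any 0–10 scale has a ceiling at 10, and no figure in the documents shows how often patients would reach it. The number of Spanish forms may be very small or zero. These points stand and limit the importance of the finding. They do not make the forms equivalent: the Spanish wording imposes a reading that the English leaves open.

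A reader might infer three stronger things that the documents do not support.

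- **A measurable bias between arms.** Assuming δ = 2 and Spanish-form splits of 3 v 1 or 4 v 1, step 4 gives 2 × 2/17 = 0.24 or 2 × 3/17 = 0.35 points. Neither the shift nor the splits has a source. The plan specifies no raw-score comparison between arms for these scales; the arm comparisons in Section 10.2 concern the OMRS and are based on response or change. Under randomisation an uneven split is chance imbalance, not systematic bias.
- **A loss of Painometer points.** O, P and Q correspond to 5 + 5 + 2 = 12 of the 49 sensory points in the key (24%). They would be lost only if a patient chose all three words and a scorer worked strictly by letter. The stated rule is by word.
- **A need to stratify by language.** With 34 evaluable patients and one stratification factor already in use, this is not a realistic expectation. Section 2.4 itself concedes that not all potential confounders can be meaningfully taken into account.

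**Conclusion.** The finding holds as a non-equivalence of translated forms. All three Spanish upper anchors refer to the patient's own experience, and none of the English ones does. If Spanish forms are used, as Section 11.6.2 anticipates, their ratings for objective 1.1.2.1 and for the correlation of OMRS with symptom scales rest on a different anchor that makes a ceiling at 10 more likely.

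The direction of the ceiling effect follows from the wording. Its size cannot be derived from the documents, and no bias figure is claimed. The primary endpoint is scored on the OMRS by trained investigators and is untouched. This is a minor point, worth making because the correction is nearly free and because ratings taken against the wrong anchor cannot be repaired later. The Painometer lettering is clerical.

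**What to change.** Render the three English upper anchors directly in Spanish, by dropping *que he sentido* from each, so that both languages end at the same plain anchor. For Spanish forms already completed, repeat the pain, sensitivity and dryness analyses without the Spanish 0–10 ratings and report both results. This requires knowing which language version each patient completed, which Appendix H does not list among the data elements to be recorded. In the same revision, reletter O, P and Q as L, M and N in the first Spanish Painometer list.

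The cost is a form revision with IRB approval and one sensitivity analysis. A few ratings are set aside in that analysis only, and there is no added burden on patients.

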#### SENSIBILIDAD ORAL

En una escala del 0 al 10, ¿qué tan SENSIBLE siente su boca en este momento? Por favor marque el número adecuado con un círculo.

0	1	2	3	4	5	6	7	8	9	10
No suf sentido		ensibilid	lad						La pec	or sensibilidad que he

#### **RESEQUEDAD ORAL**

En una escala del 0 al 10, ¿qué tan SECA siente su boca EN ESTE MOMENTO? Por favor marque el número adecuado con un círculo.

0 1 2 3 4 5 6 7 8 9 10 No siento resequedad La peor resequedad que he sentido

### Escala Global

Si compara la condición actual de su boca, con la condición en la que estaba HACE DOS SEMANAS, ¿en que condición general esta su boca? Por favor, marque con un círculo.

Mucho peor	Un poco peor	Igual	Un poco mejor	Mucho mejor
LIP Print Name	[name]	_ LIP Signature:_		
Date of Evaluation	on:			

Timepoint:\_\_\_\_\_

## 15.11 APPENDIX K: ORAL HEALTH IMPACT PROFILE (OHIP-14)

Date:	/	/	Timepoint:	LIP print name:	[name]	LIP
Signat	ure:					

#	Ha tenido los siguientes problemas, debido a dificultades con su boca, sus dientes o dientes postizos:	Nunca (0)	Casi nunca (1)	Ocasional- mente (2)	Frecuente- mente (3)	Muy frecuen- te (4)
1	¿Ha tenido dificultad al pronunciar palabras?					
2	¿Se ha empeorado el sentido del gusto ha empeorado?					
3	¿Ha estado adolorida su boca?					
4	¿Se siente incómodo al comer?					
5	¿Se siente muy consciente de sí mismo?					
6	¿Se siente tenso/a?					
7	¿Ha sido insatisfactoria su dieta?					
8	¿Ha tenido que interrumpir tiempos de comida?					
9	¿Se da cuenta que le es muy difícil relajarse?					
10	¿Se siente un poco avergonzado/a?					
11	¿Se ha sentido muy irritable hacia otras personas?					
12	¿Ha tenido dificultad haciendo cosas que usualmente ha hecho sin dificultad?					
13	¿Se siente menos satisfecho/a con su vida en términos generales?					
14	No ha podido funcionar del todo.					

Total \_\_\_\_\_

Protocol 12C0068

English version translation of Appendix J

## Painometer (POM) Assessment Sheet

Baseline		Date: _	/	/	Time	e:	Subject Study Number:
	ı intens	ity list below					the Sensory pain intensity list and the the chosen letter/word and
	SEN A B.	NSORY Cramping Dull			AF 1. 2.	FECTIVE Nagging Agonizing	
	C. D.	Splitting Burning			3. 4.	Annoying Troublesom	e
	Е. F.	Sore Shooting			5. 6.	Killing Tiring	
	G.	Radiating			7.	Unbearable	
	Н. І.	Hurting Crushing			8. 9.	Sickening Terrifying	
	J. K.	Aching Stabbing				Miserable Torturing	
	L. M.	Sharp Tearing				-	

N. Pressing

II. INSTRUCTIONS: Ask the participant to choose the word which describes the duration of oral pain and check the response:

Continuous

Periodic (Comes and goes)

III. INSTRUCTIONS: Ask the participant to choose words from the Sensory pain intensity list and the Affective pain intensity list below to describe present oral pain with swallowing Circle the letters/numbers and words chosen from the lists.

SE	NSORY
А.	Cramping
В.	Dull
C.	Splitting
D.	Burning
E.	Sore
F.	Shooting
G.	Radiating
Н.	Hurting
I.	Crushing
J.	Aching
Κ.	Stabbing
L.	Sharp

#### AFFECTIVE

- 1. Nagging
- 2. Agonizing
- 3. Annoying
- 4. Troublesome
- 5. Killing
- 6. Tiring
- 7. Unbearable
- 8. Sickening
- 9. Terrifying
- 10. Miserable
- 11. Torturing

- M. Tearing
- N. Pressing

IV. INSTRUCTIONS: Ask the participant to choose the word which describes the duration of oral pain with swallowing and (') the response

Continuous

Periodic (Comes and goes)

## Scoring of Painometer (POM) Assessment Sheet

Weighted scores for the Painometer sensory word descriptors are:

- A. Cramping = 4
- B. Dull = 1
- C. Splitting = 5
- D. Burning = 4
- E. Sore = 1
- F. Shooting = 5
- G. Radiating = 3
- H. Hurting = 2
- I. Crushing = 4
- J. Aching = 3
- K. Stabbing = 5
- L. Sharp = 5
- M. Tearing = 5
- N. Pressing = 2

Weighted scores for the Painometer affective word descriptors are:

- 1. Nagging = 1
- 2. Agonizing = 4
- 3. Annoying = 1
- 4. Troublesome = 2
- 5. Killing = 5
- 6. Tiring = 3
- 7. Unbearable = 5
- 8. Sickening = 4
- 9. Terrifying = 5
- 10. Miserable = 3
- 11. Torturing = 5

Total score is calculated by simple summation of individual weighted scores.

## Numeric Rating Scales (0-10) for Oral Pain, Sensitivity, and Dryness

#### ORAL PAIN

## On a 0 to 10 scale, how PAINFUL is your mouth now? Please circle the number.

	0	1	2	3	4	5	6	7	8	9	10
No pa	in										Worst pain

#### **ORAL SENSITIVITY**

#### On a 0 to 10 scale, how SENSITIVE is your mouth now? Please circle the number.

	0	1	2	3	4	5	6	7	8	9	10
No se sensi	ensitivity itivity	/									Worst

#### ORAL DRYNESS

## On a 0 to 10 scale, how DRY is your mouth NOW? Please circle the number.

0 1 2 3 4 5 6 7 8 9 10	0	1	2	3	4	5	6	7	8	9	10
------------------------	---	---	---	---	---	---	---	---	---	---	----

No dryness

Worst dryness

## **Global Scale**

Compared to TWO WEEKS ago, what is the overall condition of your mouth? Please circle.

Much worse

A little worse

Same A little better

Much better

## Oral Health Impact Profile (OHIP-14) 

Date: \_\_\_/\_\_/ Timepoint: \_\_\_\_\_ LIP print name: [name]\_LIP Signature: \_\_\_\_\_

						Very
	Because of problems with your teeth,		Hardly	Occasionally	Often	Often
#	denture or mouth have you	Never (0)	ever (1)	(2)	(3)	(4)
1	Had trouble pronouncing words					
2	Felt sense of taste has worsened					
3	Had painful aching in the mouth					
	Found it uncomfortable to eat any					
4	foods					
5	Have been self-conscious					
6	Felt tense					
7	Had an unsatisfactory diet					
8	Had to interrupt meals					
9	Found it difficult to relax					
10	Have been a bit embarrassed					
11	Have been irritable with other people					
12	Had difficulty doing usual jobs					
13	Felt life in general was less satisfying					
14	Have been totally unable to function					

Total\_\_\_\_\_
